6 STUDY PERIODS, TREATMENT REGIMENS AND POPULATIONS FOR ANALYSES

6.1 Study Periods

Screening for inclusion in the study will be performed up to 4 weeks before the first treatment day. After screening, study participants will be enrolled in the study according to their eligibility as per the inclusion and exclusion criteria, and will be randomized to 1 of the 6 sequences that will be conducted in parallel.

Each sequence has 3 periods. Study participants will be admitted to the study facility on the treatment day, which will be the Day 1 of each of the three periods. Study participants will remain in the study facility for approximately 3.5 hours post-dose and discharged on the same day, unless the investigator and the study team consider that an overnight stay is warranted. The treatment day of period 1 and period 2 are followed by a washout period of at least 7 days but no more than 4 weeks.

6.2 Treatment Regimens

The selection and timing of dose for each participant is as follows:

Table 5.2-1: Selection and Timing of Dose

Study Treatment	Unit dose strength(s)/Dosage level(s)	Dosage formulation Frequency of Administration	Route of Administration
BMS-986231	3 µg/kg/min for 10 min (5 mL/H) 6 µg/kg/min for 10 min (10 mL/H) 12 µg/kg/min for the rest of the 5-hour infusion (20 mL/H)	Single infusion	IV
Nitroglycerin	20 µg/min for 10 min (5 mL/H) 40 µg/min for 10 min (10 mL/H) 80 µg/min for the rest of the 5-hour infusion (20 mL/H)	Single infusion	IV
Placebo*	5 mL/H for 10 min 10 mL/H for 10 min	Single infusion	IV

Table 5.2-1: Selection and Timing of Dose

Study Treatment	Unit dose strength(s)/Dosage level(s)	Dosage formulation Frequency of Administration n	Route of Administration
	20 mL/H for the rest of the 5-hour infusion		

* Placebo will be a solution of 5% dextrose (D5W) that will be locally supplied by the sites.

6.3 Populations for Analyses

The following populations will be used for the analyses:

- **The Enrolled Population** will consist of all subjects who sign informed consent
- **The Randomized Population** will consist of all randomized subjects who have started study drug infusion in at least one treatment period. This is also known as the Intent to Treat (ITT) population. Data in this data set will be analyzed based on randomized treatments in each period.
- **The Safety Population** will consist of all subjects who take at least 1 dose of double-blind study treatment. Participants will be included in the treatment group they received in each period.
- **The Pharmacokinetic analysis dataset (PK Population)** will consist of all subjects who receive BMS-986231 and have at least one post dose PK sample. Additionally, **the Evaluable PK Population** is defined as subjects who have adequate PK profiles.

7 STATISTICAL ANALYSES

SAS® version 9.2 or higher will be used for statistical analyses, tabulations and graphical presentations. S-Plus® may be also used for graphical presentations.

7.1 General Methods

Descriptive summaries will be presented for continuous variables using number of subjects (N), mean, standard deviation (SD), median, minimum and maximum.

Descriptive summaries for categorical variables will utilize counts and percentages. Several analyses noted in subsequent sections will present 95% confidence intervals (CIs), but no pre-specified significance testing will be included.

In general, continuous variables will be analyzed using a mixed-effect model with sequence, treatment period, and treatment, and the difference in the treatment period baselines as a covariate. From the statistical modeling, the means, standard errors, and 2-sided 95% confidence intervals for the difference between BMS-986231 and the other treatment group will be presented. The analyses for efficacy and exploratory endpoints will use a nominal level of

$\alpha=0.05$ for inference with no multiplicity adjustment. The nominal p-value for comparing two treatments will be provided as well.

Adverse events and medical history will be coded according to the most recent Medical Dictionary for Regulatory Activities (MedDRA) version. Previous and concomitant medications will be coded using the WHO Drug Dictionary.

For analyses involving baseline, the baseline value is defined by the last value prior to the start of infusion for a specified period, unless otherwise noted.

7.2 Study Conduct

Protocol deviations identified as significant will be captured in a trial management system and reported in the CSR. Relevant protocol deviations are those that are programmable and could potentially affect the interpretability of the study results. The following protocol deviations will be defined as **relevant protocol** deviations and listed:

- Error in treatment assignment resulting in a subject being dosed with an incorrect treatment
- Systolic blood pressure (SBP) < 115 mm Hg at screening or pre-randomization
- Violation of inclusion criterion 2 (b): Subjects do not have heart failure with reduced ejection fraction or have no LVEF on echocardiogram of 40% or less.
- Violation of exclusion criterion 1 (a): Subjects have Systolic blood pressure (SBP) < 115 mm Hg at screening or pre-randomization.
- Violation of exclusion criterion 1 (b): Subjects have heart rate < 50 beats per minute (bpm) or > 90 bpm at screening or pre-randomization.
- Violation of exclusion criterion 3 (a): Subjects have treatment with oral phosphodiesterase type 5 (PDE5) inhibitor sildenafil, vardenafil or avanafil within 24 hours of study drug infusion or treated with tadalafil within 4 days of study drug infusion.
- Violation of exclusion criterion 4 (a): Subjects have estimated glomerular filtration rate (eGFR) < 15 ml/min/1.73 m².

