2 SCHEDULE OF ACTIVITIES

Table 2-1: Time & Event Schedule CV013020, Screening Period

Procedure	Screening Visit	Notes
Eligibility Assessments		
Informed Consent	x	A participant is considered enrolled only when a protocol specific informed consent is signed.
Inclusion/Exclusion Criteria	x	
Medical History	x	
Concomitant medications	x	
Echocardiography eligibility assessment	x	As described in the echocardiographic core lab manual, evaluation of image quality and assessment of ejection fraction
Safety Assessments		
Physical Examination	x	If the screening physical examination is performed within 3 days prior to first dosing then a single exam may count as both the screening and pre-dose evaluation. Includes height and weight.
Vital Signs	x	Includes body temperature, respiratory rate, and seated blood pressure and heart rate. Blood pressure and heart rate should be measured after the participant has been resting quietly for at least 5 minutes.
Adverse Events Assessment	x	SAEs must be collected from the date of the participant's Informed consent.
Local Laboratory Tests	x	Hematology, Serum chemistry, NT-proBNP or BNP (details in the protocol section 9.4.4)
Pregnancy Test (WOCBP only)	x	

Table 2-2: Time & Event Schedule CV013020, Treatment and Follow-up Study Periods

Procedure	Treatment Period					Notes
	Period 1 Day 1	Washout 5-28 Days	Period 2 Day 1	Washout 5-28 Days	Period 3 Day 1	
Safety Assessments						Washout between periods should be at least 5 days and no more than 4 weeks.
Weight	x		x		x	Weight pre-and end of the infusion in each treatment period.
Targeted physical examination	x		x		x	Based on subject's report since the screening visit. Includes temperature, signs and symptoms of congestion.
Vital Signs (Blood pressure and heart rate)	x		x		x	Prior to infusion. 30 minutes at first hour, then every 1 hour until discontinuation of infusion, then at 1 hour, 2 hour and 3.5 hour after end of infusion in each treatment period.
Peripheral Oxygen Saturation	x		x		x	Prior and end of the infusion in each treatment period, measured with a pulse oximeter device.
12 lead ECG	x		x		x	Prior to the infusion and after end of infusion in each treatment period.
Urinary output	x		x		x	From start of infusion to 3 hours after end of infusion in each treatment period.
Telemetry	x		x		x	From start of infusion to 3 hours after end of infusion in each treatment period.

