Whole body bioimpedance	x		x		x	Prior to infusion, at 1 hour and 3 hours after start of infusion, at end of infusion and 2 hours after the end of the infusion in each treatment period. In addition, should be performed after each supplementary echocardiographic assessment.
Pulse wave analysis	x		x		x	Prior to and at end of infusion in each treatment period, just after the echocardiographic assessment has been performed. In addition, should be performed after each supplementary echocardiographic assessment.
Administer Study Medication	x		x		x	5-hour continuous infusion *Study medication to begin promptly after pre-infusion testing completed*
Clinical Drug Supplies						
Randomize	x		x		x	
Dispense Study Drug	x		x		x	
Additional Research Sampling						
Additional Research plasma	x		x		x	Sampling will be done pre-dose and 4.5 hours after the start of the infusion in each treatment period.
Blood sampling for DNA variants in mARC and ADME related genes	x					Sample can be collected at Period 1 Day 1 or any other day, only one sample collection for each subject during the study.

In the event of multiple procedures are required at a single time point, the following order for performing the procedures is recommended:

Revised Protocol No.: 05
Date: 24-Jan-2019

Approved v6.0 930114837 6.0

- Safety
- Pharmacokinetic sampling
- Additional research sampling

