6.2 Exclusion Criteria

1) Target Disease Exceptions

- a) Systolic blood pressure (SBP) $<$ 110 mm Hg at screening or pre-randomization
- b) Heart rate $<$ 50 beats per minute (bpm) or $>$ 90 bpm at screening or pre-randomization
- c) Permanent Atrial Fibrillation, Atrial Flutter or having Atrial Fibrillation, Atrial Flutter before start of the infusion
- d) Permanent paced rhythm (VVI, DDD or BiV pacing)
- e) NYHA Class IV symptoms of heart failure

2) Medical History and Concurrent Disease

- a) Primary HF etiology attributable to either restrictive/obstructive cardiomyopathy, idiopathic hypertrophic or uncorrected severe valvular disease as defined by AHA/ACC/ESC criteria. (Note: A restrictive mitral inflow pattern is not exclusionary)
- b) Pericardial tamponade or constrictive pericarditis
- c) Large post-MI LV aneurisms
- d) Intra-cardiac thrombus
- e) Prior mitral valve repair, mitral or aortic prosthesis of any type.
- f) LV assist device or prior heart transplant
- g) Hospitalized for acute decompensated heart failure in the previous month
- h) Hospitalized with acute coronary syndrome, coronary revascularization or acute myocardial infarction during the previous 90 days prior to screening
- i) Have a history of a cerebral vascular accident (CVA or stroke) or of a transient ischemic attack (TIA) during the previous 90 days prior to screening
- j) Considered clinically unstable for any condition
- k) Serious comorbid non cardiovascular disease in which the life expectancy of the subject is < 3 months
- l) Liver disease defined as history of cirrhosis with evidence of portal hypertension such as varices, or encephalopathy, or total bilirubin > 3 mg/dL (> 51 µmol/L) or significant elevation of liver enzymes (AST, ALT > 3 times the upper limit of normal)
- m) Prior solid organ transplant

3) Prior/Concomitant Therapy

- a) Treatment with oral phosphodiesterase type 5 (PDE5) inhibitor sildenafil, vardenafil or avanafil within 24 hours of study drug infusion or treated with tadalafil within 4 days of study drug infusion
- b) Treatment with intravenous inotropic therapy (dobutamine, milrinone, levosimendan) in the previous month or planned treatment in next 3 months.
- c) Current treatment with chronic oral, transdermal or sublingual nitrates, except at the discretion of the investigator and treating physician, nitrates could be temporarily interrupted. In which case, an interruption of 3 days is required prior to start of study drug.

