2 STUDY DESCRIPTION

2.1 Study Design

This is a multi-center, randomized, cross-over, placebo and active-controlled, double-blind, study of continuous 5-hour intravenous (IV) infusions of BMS-986231 in patients with heart failure and reduced ejection fraction (HFrEF). The trial is designed to evaluate the effects of BMS-986231 on systolic and diastolic parameters measured by echocardiography.

A cross-over design will be implemented in this trial; every subject will be exposed to each of the 3 interventions (BMS-986231, Nitroglycerin (NTG) and placebo) in 3 treatment periods. Each treatment period will include one intervention occurring via 5-hour infusion, followed by a washout period of at least 7 days, but no more than 4 weeks.

42 study participants will be randomized to receive BMS-986231, NTG, and placebo, in one of the 6 possible sequences.

NTG, BMS-986231 and placebo will be administered as a 5-hours infusion according to an uptitration schedule, which is achieved by an increase in the infusion flow rate. All three interventions (NTG, BMS-986231 and placebo) will have the same flow rate: 5 mL/H for 10 min, followed by 10 mL/H for 10 minutes then 20 mL/H for the rest of the infusion.

[figure not shown]
The corresponding doses of the active study medications will be:

- NTG: 20 $\mu\text{g}/\text{min}$ for 10 min, followed by 40 $\mu\text{g}/\text{min}$ for 10 min, followed by 80 $\mu\text{g}/\text{min}$ for the rest of the 5-hour infusion;
- BMS-986231: 3 $\mu\text{g}/\text{kg}/\text{min}$ for 10 min, followed by 6 $\mu\text{g}/\text{kg}/\text{min}$ for 10 min, followed by 12 $\mu\text{g}/\text{kg}/\text{min}$ for the rest of the 5-hour infusion.

In case of a decrease in systolic blood pressure, an algorithm will be used to down-titrate /interrupt or discontinue the study drug infusion (see protocol [Section 7.4](#)).

The study design schematic is presented in Figure [2.1-1](#).

Figure 2.1-1: Study Design

*Wash-out period will be at least 7 days and no more than 4 weeks

Screening

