2.4 Protocol Amendments

This statistical analysis plan (SAP) is based on the revised protocol version 02, which incorporates Amendment 02, dated 01-Sep-2017.

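### SAP 7.2 flags exclusion criterion 1(a) at SBP below 115 mm Hg, but the current protocol sets it at below 110, so eligible participants at 110–114 would be listed as violators

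*SAP*

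**What the plan says.** SAP 7.2 lists the protocol deviations that will be programmed and listed as relevant, meaning those that could affect how the results are interpreted. One is "Violation of exclusion criterion 1 (a): Subjects have Systolic blood pressure (SBP) < 115 mm Hg at screening or pre-randomization". The same list also carries a separate bullet with the same 115 mm Hg cut-off and no criterion number.

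Protocol 6.2, exclusion criterion 1(a), excludes participants whose systolic pressure is below "110 mm Hg at screening or pre-randomization". The synopsis gives the same limit.

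On versions, SAP 2.4 states: "This statistical analysis plan (SAP) is based on the revised protocol version 02", dated 01-Sep-2017. The protocol supplied carries the footer "Revised Protocol No.: 05", dated 24-Jan-2019.

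A second figure also differs. Under Figure 2.1-1 the SAP states "Wash-out period will be at least 7 days and no more than 4 weeks". SAP 2.1 and 6.1 say the same (6.1: "followed by a washout period of at least 7 days but no more than 4 weeks"). Protocol Table 2-2 states "Washout between periods should be at least 5 days and no more than 4 weeks", and the synopsis and section 5.1 agree with it.

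**The concern.** A deviation that cites a criterion by number should apply that criterion's limit. Here the SAP names 1(a) and then uses a limit 5 mm Hg higher than the one in the current protocol. A participant who met the entry criterion would appear in the study report's listing of relevant deviations as someone who should not have been enrolled. That misreports trial conduct in an output which the SAP itself reserves for deviations bearing on interpretability.

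The stake is accuracy of reporting. It does not extend to the treatment comparison.

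**Working it through.** **1. The two rules side by side**

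| Item | SAP 7.2 | Protocol synopsis and 6.2 |
|---|---|---|
| Criterion cited | Exclusion 1(a) | Exclusion 1(a) |
| When measured | Screening or pre-randomization | Screening or pre-randomization |
| Cut-off | SBP < 115 mm Hg | SBP < 110 mm Hg |

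The measurement and its timing are the same, and only the number differs. In whole mm Hg:

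- flagged by the SAP but not excluded by the protocol: 110, 111, 112, 113, 114
- excluded by the protocol but missed by the SAP: none

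**2. Is the mismatch isolated?**

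SAP 7.2 has five bullets tied to a numbered criterion. Four agree with Revised Protocol 05:

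- 2(b): LVEF 40% or less
- 1(b): heart rate below 50 or above 90 bpm
- 3(a): the PDE5 inhibitor windows
- 4(a): eGFR below 15

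Only 1(a) does not agree.

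**3. Does any analysis use the flag?**

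SAP 6.3 defines enrolled, randomized, safety, PK and evaluable PK populations. None is a per-protocol set. For the randomized population it says: "Data in this data set will be analyzed based on randomized treatments in each period". SAP 7.5.1 and 7.5.2 summarise efficacy for all randomized subjects. The cut-off therefore changes the deviation listing and nothing else.

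**4. How many participants could be affected?**

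The plan gives no figure to reproduce and no SBP distribution, so what follows is illustration only. Assume one normal reading with mean 120–130 and SD 12–15 mm Hg, truncated at 110 because lower values are excluded. With Φ the standard normal distribution function, m the mean and s the SD:

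P(110 ≤ SBP < 115 | SBP ≥ 110) = [Φ((115 − m)/s) − Φ((110 − m)/s)] / [1 − Φ((110 − m)/s)]

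For m = 120 and s = 12 this is (0.3385 − 0.2023) / (1 − 0.2023) = 0.171, and 0.171 × 42 = 7.2.

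| Mean / SD | Share at 110–114 | Of 42 |
|---|---|---|
| 120 / 12 | 17.1% | 7.2 |
| 120 / 15 | 15.6% | 6.6 |
| 125 / 12 | 10.8% | 4.5 |
| 125 / 15 | 11.2% | 4.7 |
| 130 / 12 | 6.1% | 2.6 |
| 130 / 15 | 7.4% | 3.1 |

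The bullet covers two occasions, so either reading can trigger the flag. Assume two bivariate normal readings with correlation 0.5–0.9:

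P(at least one < 115 | both ≥ 110) = 1 − P(both ≥ 115) / P(both ≥ 110)

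- lowest, at 130/12 and correlation 0.9: 1 − 0.8619/0.9347 = 7.8%, or 3.3 of 42
- highest, at 120/12 and correlation 0.5: 1 − 0.5101/0.6840 = 25.4%, or 10.7 of 42

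All these counts suppose that all 42 were randomised under the 110 criterion. If only a fraction were, each count falls in proportion, down to 0.

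**The case against.** The strongest reply is that the SAP may be faithful to its stated source. Revised Protocol 02 is not available here, and the visible history does not show whether 115 applied under an earlier version or when 110 took effect. A flag at 110–114 would be correct for someone randomised under a version with a 115 limit. That stands. It is why the conclusion is confined to participants randomised under the 110 criterion, and why the fix follows the version in force at randomisation and does not simply substitute 110 throughout.

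It can also be said that this is housekeeping. The flag feeds a listing only, no genuine violation below 110 is hidden, and SAP 7.2 reports significant deviations separately through the trial management system. The limited reach is accepted. But the bullet is an operative programming rule for a planned output, and it would give a wrong result for the participants described.

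Two further points are fair. The counts above rest wholly on assumed distributions, and the mismatch itself does not depend on them. The washout difference has no bearing on the deviation listing: no washout-compliance output is planned, so it is a conflict between documents and adds no weight to the SBP point.

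**Conclusion.** The concern holds. SAP 7.2 applies a 115 mm Hg limit to a criterion that the current protocol sets at 110. Participants validly randomised under the 110 criterion with SBP 110–114 would be listed as violating it. The contradiction is certain from the text. The number of participants it touches is not known: from 0 to about 11 of 42 across the assumptions shown, depending on the SBP distribution, on whether one or two readings count, and on how many were randomised under the 110 criterion.

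The effect is confined to the relevant-deviation listing. It should be corrected, but it does not threaten the primary or secondary inference. Nothing here judges which SBP limit or which washout is clinically right.

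**What to change.** Before database lock:

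- Derive the 1(a) deviation from the criterion in the protocol version in force when each participant was randomised, using a threshold looked up by version.
- Delete the unnumbered SBP bullet in SAP 7.2, which duplicates the 1(a) bullet.
- Update SAP 2.4 to the current protocol version.
- Reconcile the minimum-washout statements in SAP 2.1, Figure 2.1-1 and 6.1 with those in protocol sections 1, 2 and 5.1.

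The cost is a SAP amendment and a small programming change to one listing. No new data are needed.

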7.3 Study Population

1.1.1 Subject Disposition

Subject disposition will be listed. Summary tables reflecting the number of subjects who are enrolled, who are randomized, and reasons for not being randomized, will be presented as overall.

The number of subjects who do not complete each treatment of 5 hours infusion, both overall and according to reasons for discontinuation from the treatment, will be summarized for safety population. Subjects who have temporary interruption or down-titration of study drug but do not discontinue permanently will be analyzed as completing the treatment. The number of subjects who do not complete the study phase, both overall and according to reasons for not completing, will be summarized for safety population, as overall and by treatment group.

1.1.2 Demographics and Baseline Characteristics

Frequency distributions and summary statistics for demographic and baseline variables will be presented for all enrolled subjects. Demographic variables to be summarized include: age, gender, race, ethnicity, and region.

Baseline variables to be summarized include the following:

- Physical measurements (height, body weight, body mass index)
- Vital signs (body temperature, respiratory rate, systolic and diastolic blood pressure and heart rate)

1.1.3 Physical Measurements

Physical measurements such as body weight and height will be summarized by nominal visit for the safety population, as overall and by treatment group. Measurements will also be listed for all treated subjects.

1.1.4 Medical History and Previous Medications

Medical history and previous medications taken prior to dosing will be listed for the safety population.

7.4 Extent of Exposure

At any time during the administration of study drug, the study drug infusion must be discontinued if an adverse event or any other safety issue suggests it is not in the patient's best interest to continue to receive study drug.

The investigator has the option to adjust the study drug dosage level downward by 50%, interrupt, or discontinue the study drug infusion in patients that develop hypotension, or if the patient experiences symptomatic hypotension that is not easily tolerated, as follows

- Study drug reduction: Study drug is decreased by 50% if SBP decreases to levels <90 mmHg but ≥ 80 mmHg. The dose cannot be subsequently increased.
- Study drug interruption: Study drug is interrupted for 1 hour if SBP decreases to <80 mmHg or symptoms of low blood pressure occur within the first 4 hours of infusion. If the SBP is ≥ 105 mmHg after one hour interruption, the study drug could be resumed at 50 % of the dose to complete 5-hours of effective study drug infusion.
- Study drug discontinuation: Study drug will be permanently discontinued if SBP remains < 105 mmHg after 1 hour interruption or if SBP decreases to levels <80 mmHg or symptoms of low blood pressure occur after 4 hours of infusion.

End of infusion procedures should be done as soon as possible after interruption or discontinuation of the study drug. If an infusion in a given period is discontinued, patients remain eligible to complete subsequent periods.

Study drug administration and randomization schedule will be documented as per subject listings. The number and percentage of subjects with dose interruptions, dose reductions, and

dosing discontinuations will also be summarized and listed by treatment group for the safety population.

Any non-study medications taken by subjects, any conducted non-study medical treatment procedures, and any utilized non-study diagnostic procedures will also be listed.

